4.3 RANDOMISATION

Participants will be allocated into one of four trial arms following baseline assessments, using stratified randomisation (Suresh, 2011), based on gender, BMI, and free sugar intakes (%TEI) at baseline, as variables that may affect our outcomes. Randomisation will be undertaken by a researcher with no direct contact with participants using a random number generator, before the trial start. Group allocations will be concealed using opaque envelopes.

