This updated data from CSV2 was copied into a new file named CSV4. In CSV4 a helper column combining the participants ID number and log day (eg: JS19900.1, combination of JS1990 and 0.1) was used in combination with a new sheet to summarise all nutrients for each participant and each diet diary day. This resulted in 5120 unique daily totals across all nutrients. The CSV4 file was then saved as complete. Including all participants and screened non-participants a total of 70747 individual diary entries on the study via Nutritics Libro. Of these data, 67546 were participant entries and 3201 from non-participant screening diaries, with a total of 10757 unique food items logged.

Sweetener and sweet food counts

Foods that contained sweeteners, were high, medium or low in sugar were separated into counts for each diet diary. These counts were then added into 5 separate scores for the summation of foods consumed in each category for baseline, timepoints 1-4 and endpoint.

ALL DATA - MULTIPLE IMPUTATION

Main analyses were completed on an intention to treat basis as the gold standard for representing the applicability of the intervention in a real world setting rather than an ideal outcome. A variety of techniques to replace/analyse RCT results with missing data have been previously utilised including complete case analysis (CCA), single imputation (SI)(by last observation carried forward, mean or regression), multiple imputation or mixed-effect models (Bell et al., 2014; Li & Stuart, 2019; Ren et al., 2022). CCA and SI methods were discounted due to CCA not being reflective of real-world data, reducing statistical power and SI lacking uncertainty and most likely underestimating variance.

Instructions for the steps used to complete MI and the imputation sequence are included below. As multiple imputation is completed in the order of the variables within the analysis, the variables list was set as randomisation variables first, then nutrient values, anthropometrics and finally questionnaire data in the order that they were completed. All baseline variables were used as predictors, all endpoint variables used as imputations only due to the monotonic pattern.

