BLNFS, BLDGendermale1female2, BLBMI, BLNEnergykcal, BLNCarbohydrateg, BLNProteing, BLNFatg, BLN Sugarsg, BLNFreeSugarsg, BLNFibreg, BLNSaturatedFatg, BLSSodiumNamg, BLWeightkg, BLWaistcircumferencecm, BLLTEShealthscore, BLFCQ1Health, BLFCQ2Mood, BLFCQ3Convenience, BLFCQ4SensoryAppeal, BLFCQ5NaturalContent, BLFC1Q6Price, BLFCQ7WeightControl, BLFCQ8Familiarity, BLFCQ19EthicalConcern, BLSQPC1Personalimpact, BLSQPC2Personalmanagement, BLSQPC3Nonchalance, BLSQPC4Negativity, BLSQPC5Perceivedunderstanding, BLSQPC6PerceivedNonautonomy, BLSF36PCS, BLSF36MCS, BLTSEQ CR, BLTSEQQUE, BLTSEQEE. *Followed by imputation only variables

Get pooled descriptives for analysis / comparison to my values.

1. Data - Split file
 - a. Click split file in ComA1_imp
 - b. Click compare groups
 - c. By imputation number_variable
 - d. Ok
2. Analyze – Descriptive statistics
 - a. Descriptives
 - b. Input all BL and EP variables apart from BL OG FS%.
 - c. Scroll to bottom of output table for pooled means – SD will be calculated from average of 20 imputations at a later date and are not shown here.

BLINDING

The main researcher had no knowledge of allocated groups of participants and was blinded during all data handling and imputation.

DATA ANALYSIS

Outcomes

Primary outcomes were % TEI from free sugars (%FS), and adherence to the recommendations at 12 weeks. Secondary outcomes were dietary profiles (daily energy intake, dietary composition, food consumption), anthropometry, sweet food perceptions and preferences, sweet food choice, attitudes to sweet foods, attitudes towards eating behaviour, motives for food choice, knowledge and lifestyle variables, quality of life and adverse events at week 12; change between baseline and week 12 in key outcomes (%FS, daily energy intake, sugar-sweetened and sweetener-sweetened food consumption, anthropometry), %FS, adherence, dietary profiles and barriers and facilitators towards intervention adherence and success/failure in achieving the recommendations (subset only) at weeks 1, 2, 4 and 8. Demographic variables, and sweet taste sensitivity, sweet liker status and PROP (bitter taste) status were also assessed at baseline, to aid in the interpretation of all outcomes, considering associations between these variables and sweet taste perceptions, liking and food intakes (Jayasinghe et al., 2017; Yeomans et al., 2009).

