Primary models will include gender, age, control/intervention group, baseline %FS, baseline body weight (as randomization variables), and baseline variable of interest. In analyses for %FS, sugar-sweetened food intake, LCS-sweetened food intake, body weight and waist circumference, TEI at Week 12 and physical activity at Week 12 will also be included. Secondary models will also include any additional variable that correlates with each outcome when assessed independently. All variables measured will be considered as secondary variables. Effects for all continuous variables will be investigated using linear multiple regression. Effects for adherence will be investigated using logistic regression to predict adherent vs not adherent.

Analyses Two: Quantitative Data

For analyses two, analyses one will be repeated for demographic groups where significant associations for these variables were found in analyses one. Analyses will only be conducted if significant associations are reported. If no significant associations with demographic variables are found, these analyses will not be completed. These analyses are intended to demonstrate differing effects of the intervention/s in different population groups.

Analyses Three: Qualitative Data

Analyses three will investigate the qualitative data collected from a subset of participants using solo interviews. These interviews were scheduled for completion in a sample of 80 participants from different intervention groups and at different time points. These analyses will be undertaken using a thematic framework analysis. First, a random sample of interviews will be analysed inductively using thematic analysis to identify codes. These codes will be used to create a framework and the framework then applied to all interviews.

Framework analysis has been chosen as a suitable analytical method for evaluating the qualitative interview data gathered, due to an interest in individual experiences and seeks to identify the different factors (barriers or facilitators) that contributed to successful or unsuccessful dietary change (Braun & Clark, 2013). The practical methods for conducting framework analysis follow a methodology as outlined below.

Framework analysis (Braun & Clarke, 2006; 2013; Gale et al, 2013).

Phase 1 'Familiarizing yourself: Transcribing data (if necessary), reading and re-reading the data, noting down with your data: initial ideas'.

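### The SAP's primary models carry body weight under the label of a randomisation variable, while BMI, the variable the protocol stratifies on, is in none of them

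*SAP*

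**What the plan says.** Protocol section 4.3 allocates participants "using stratified randomisation (Suresh, 2011), based on gender, BMI, and free sugar intakes (%TEI) at baseline". Age and body weight are not in that list.

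The SAP's multiple imputation section agrees with the protocol. It says "the variables list was set as randomisation variables first", with nutrients, anthropometrics and questionnaires following. The sequence printed later begins "BLNFS, BLDGendermale1female2, BLBMI". Body weight appears further down, next to waist circumference.

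The SAP's analysis section departs from both: "Primary models will include gender, age, control/intervention group, baseline %FS, baseline body weight (as randomization variables"), followed by the baseline variable of interest. For %FS, the two sweet-food intakes, body weight and waist it adds that "TEI at Week 12 and physical activity at Week 12 will also be included". BMI is not mentioned.

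Two other SAP rules bear on the point. Secondary models take in any measured variable that correlates with the outcome when assessed alone. Under Data presentation, variables in multiple regressions are checked for multicollinearity against a correlation cut-off of 0.7.

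**The concern.** The protocol chose its stratifiers as "based on gender, BMI, and free sugar intakes (%TEI) at baseline, as variables that may affect our outcomes". Stratifying on a prognostic variable balances the arms on it. The gain reaches the test of the arm effect only if the variable is also in the model; otherwise its variation stays in the error term, and in a linear model the standard error is larger than the design warrants.

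The sentence governs both primary outcomes and the key secondary ones. If it is followed as written, the report will say that the models adjust for the randomisation variables when, on the protocol's account, one of the three is missing and another variable stands in its place.

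**Working it through.** **1. The three lists side by side**

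| Variable | Stratifier (Protocol 4.3) | Heads the SAP imputation sequence | In SAP primary models |
|---|---|---|---|
| Gender | yes | yes | yes |
| Baseline %FS | yes | yes | yes |
| BMI | yes | yes | **no** |
| Body weight | no | no (anthropometrics block) | **yes** |
| Age | no | no | yes |

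Two of the three sources agree, and only the primary-model sentence differs.

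**2. Can BMI enter by another route?**
- As baseline variable of interest: no. The anthropometric outcomes named for Analyses One are body weight and waist circumference, not BMI.
- As an outcome-specific addition: no. Those are week 12 energy intake and physical activity.
- In a secondary model: possibly, if it correlates with the outcome. Body weight is already present, so if weight and BMI correlate at 0.7 or above, the collinearity rule may keep BMI out even there.
- In the body-weight model, weight is both the labelled randomisation variable and the baseline variable of interest, so it is listed twice and BMI has no term.

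**3. Size in the linear models**

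Let r be the partial correlation of BMI with the outcome given the other covariates, body weight included. Omitting BMI multiplies the arm standard error by about 1/√(1 − r²). The documents do not give r, so the values are assumptions:
- r = 0.1: 1/√0.99 = 1.005, or 0.5% wider
- r = 0.2: 1/√0.96 = 1.021, or 2% wider
- r = 0.3: 1/√0.91 = 1.048, or 5% wider

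**4. Simulation of one two-arm contrast**

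Inputs from the protocol: 60 per arm less 20% attrition = 48 per arm, stratified on gender, BMI and %FS. Assumed inputs: BMI and %FS each split at the median, a %FS–outcome coefficient of 0.4, weight–BMI correlation 0.7 or 0.85, and a true effect of 0.5 SD for power. There were 3,000 runs per setting.

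| BMI–outcome correlation | SE, weight in model | SE, BMI in model | Power, weight | Power, BMI |
|---|---|---|---|---|
| 0.1 | 0.186–0.187 | 0.186–0.187 | about 74% | about 75% |
| 0.3 | 0.180–0.183 | 0.177 | 77% | 78–79% |
| 0.5 | 0.166–0.174 | 0.157 | 83–84% | 88–89% |

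Type I error at a nominal 5% was 3.9–5.1% with weight and 4.3–5.2% with BMI. Monte Carlo error is about √(0.05 × 0.95/3000) = 0.4 percentage points. With neither variable it fell to about 3% at correlation 0.5. Any departure is therefore towards conservatism.

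The two methods agree. At correlation 0.3 and weight–BMI correlation 0.7, residual variance is 0.84 − 0.09 × 0.49 = 0.796 with weight and 0.84 − 0.09 = 0.75 with BMI. The ratio √(0.796/0.75) = 1.03 matches the simulated 0.183/0.177 = 1.03.

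**5. The adherence outcome**

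Adherence is analysed by logistic regression. There, omitting a prognostic covariate pulls the log-odds ratio towards zero and makes its standard error smaller, so the formula in step 3 does not apply. With assumed inputs (120 people in two arms, weight–BMI correlation 0.85, BMI log-odds 0.5 per SD, true arm log-odds ratio 1), the mean standard error was 0.392 with weight and 0.396 with BMI, and power was 75.8% with either.

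**The case against.** The strongest reply is that little is lost. BMI is weight over height squared, so with weight and gender in the model what is left out is essentially height within gender. Protocol section 8.1 commits only to trial arm and the baseline outcome, with further variables as possible, and never promises adjustment for stratifiers. BMI also has a conditional route into the secondary models. All of this stands and limits the size of the point. It does not explain why the SAP calls body weight a randomisation variable.

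It can also be said that the protocol may not describe what was done. That is fair: the documents conflict, so the randomisation record should be checked first.

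Four stronger readings are tempting but unsupported:
- **Age is mislabelled too.** The list also contains trial group, so the parenthesis cannot cover every item. The label plainly attaches to body weight; for age it is only arguable, and age is a legitimate covariate.
- **The primary tests are invalid or biased.** The simulations show no type I error inflation, and no bias in the linear models has been demonstrated.
- **Weight and waist suffer most.** Their models already contain baseline weight, and the waist model baseline waist, which would be expected to absorb most of what BMI predicts. Nothing in the documents supports a larger r.
- **The wrong baseline %FS is used.** A descriptives step says "Input all BL and EP variables apart from BL OG FS"%. A reader might infer that this is the value used at allocation, before foods were recoded. Neither document defines it, so it cannot support a change to the models.

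**Conclusion.** The inconsistency is certain on the text: the primary-model sentence disagrees with Protocol section 4.3 and with the SAP's own imputation order, and BMI is in no primary model for any named outcome.

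The consequence is a small loss of precision in the linear models, about 0.5% to 5% on the standard error for an assumed r of 0.1 to 0.3. In the simulation the power loss was about 1 point or less at a BMI–outcome correlation of 0.1 and about 4 to 6 points at 0.5, the largest value tried. For adherence, the one setting examined showed no difference in power. These sizes rest on assumed correlations and on section 4.3 describing the randomisation as carried out. This is a matter of precision and accurate reporting, not of false positives, and it is worth correcting because the correction is nearly free.

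**What to change.** 1. Confirm from the randomisation record which variables, and which categories of each, set the strata.
2. If they are as in Protocol section 4.3, reword the primary-model sentence to: *gender, baseline BMI and baseline %FS (the randomisation variables), trial group, age, and the baseline variable of interest*. If weight was in fact used, correct section 4.3 and the imputation text instead.
3. In the body-weight model, keep baseline weight once, as the baseline variable of interest, alongside BMI.
4. State that stratifiers are not removed under the 0.7 cut-off. This matters most in the weight and waist models, where BMI may well exceed it.
5. Ask the sponsor to define the separate baseline free-sugar variable named in the descriptives step. Do not add it to the models on present evidence.

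The cost is one or two sentences of SAP text. BMI is already collected and in the imputation file. Replacing weight with BMI uses no extra degree of freedom, and the body-weight model uses one more, out of N = 242.

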6.4 OUTCOME ASSESSMENT SCHEDULE

An overview of the outcome assessment schedule is given in **Table 2**.

Free sugar intakes and adherence will be assessed throughout the intervention period as given in **Table 1**. All other outcomes will be assessed at baseline and at trial end, with the exception of the following: sweet liker status, PROP taste sensitivity and demographic characteristics will be measured only at baseline; questions on adherence and difficulties will be asked at weeks 4, 8 and 12.

All participants will undertake all measures, in the same manner, regardless of intervention arm. Dietary assessments, questions on adherence and difficulties will be undertaken via the Nutritics software. Self-report questionnaires will be administered online via Qualtrics. Measures associated with taste status and appetite will be presented to participants using a paper format to be completed during a test session.

Compliance with trial measures will be enhanced using a bogus pipeline method (Hugh, 2013; Muhlheim et al., 1997; Reid et al., 2014); participants will be asked to provide a saliva sample at baseline and at trial end, for the supposed purpose of examining salivary enzymes that may vary with dietary change. In reality, samples will be discarded. Only at the end of the trial will participants be informed that their samples have not been analysed.

Table 2: Schedule of enrolment, interventions and assessments

	Trial period						
	Enrolment	Baseline	Intervention			End	
Time point	Wk -1 / 2	0	Wk 1	Wk 2	Wk 4	Wk 8	Wk 12
Enrolment							
Eligibility screen	X						
Informed consent	X						
Allocation		X					
Intervention							
Intervention groups							→
Control group							→
Assessments							
24hr diet diary							→
3 day diaries	X	X					X
Adherence							→
Adherence questions					X	X	X
Anthropometrics		X					X

Sweet liker status		X					
PROP taste test		X					
Sweet taste test		X					X
Sweet food choice		X					X
Sweet attitudes		X					X
TFEQ		X					X
FCQ		X					X
Demographics		X					
Knowledge		X					X
GSLTPAQ		X					X
SF36		X					X
Adverse events							→
Difficulties / Adverse events					X	X	X
Interview			X*	X*	X*	X*	X*
BP cheek swab	X						X

X* Interviews completed only once. TFEQ: Three-factor eating questionnaire; FCQ: Food choice questionnaire; GSLTPAQ: Godin- Shepard leisure time physical activity questionnaire; SF-36: Short-form 36 measure of quality of life; BP: Bogus pipeline method.

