8 ANALYSES

The data gathered will contribute to three distinct analyses: 1) Analyses of the population as a whole to investigate the effects of the three different dietary recommendations versus control; 2) Analyses of the effects of the dietary recommendations in different population subgroups, and 3) Investigation of the barriers and facilitators to success. Quantitative data will be analysed using SPSS, on an Intention-to-Treat basis, following checks for the assumptions for parametric data. Qualitative data will be analysed as detailed below.

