8.1 ANALYSES ONE: EFFECTS OF THE DIFFERENT DIETARY RECOMMENDATIONS

To test the effects of the different dietary recommendations, a series of multiple regression analyses will be run. A separate analysis will be run for each outcome variable, where the outcome at week 12 will be predicted by trial arm (intervention/control) and outcome variable at baseline. Additional independent variables will also be included in each analysis as possible, to include: demographic variables, total energy intakes, sweet liker status; PROP taster status; and attitudes to sweet foods, eating behaviour and food choice.

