Three distinct analyses were pre-specified in advance: 1) Analyses of the population as a whole to investigate the effects of the three different types of dietary recommendation versus control; 2) Analyses of the effects of the dietary recommendations in different population subgroups, and 3) Investigation of the barriers and facilitators to success.

Data presentation

Data will be presented as mean \pm standard deviation in all cases, unless stated. Values will be considered significant at the $p<0.05$ level. Before completing analyses, data will be checked for normality. The data set is large, $N=242$, thus a normal distribution will be assumed. Where assumptions of homogeneity of variance are violated (Levene's test $p<0.05$), statistics will be taken from analyses conducted assuming non-equal variances. Bonferroni corrections for multiple testing will be applied to data where tests were not pre-specified in the study protocol. Where multiple regression analyses are used, all variables will be checked for multicollinearity using correlation cut-offs of <0.7 . Pearson correlation values will be used for all continuous variables, and Spearman correlations for categorical variables.

Participant characteristics

Details of study completion will be provided and a CONSORT diagram created detailing number randomized to each group, number completing the study in each group, drop out and number included in all analyses.

Characteristics will be given for the whole sample and for each trial group.

Analyses One: Quantitative Data

For analyses one, multiple regression analyses will be used. Analyses will be conducted for both primary outcomes, for key secondary outcomes - daily energy intake, sugar-sweetened food intake, LCS-sweetened food intake, body weight, waist circumference, and adverse events; and change (baseline - week 12) data for these outcomes; and for other secondary outcomes (dietary

composition, sweet food perceptions and preferences, sweet food choice, attitudes to sweet foods, attitudes towards eating behaviour, motives for food choice, knowledge and lifestyle variables, quality of life) if differences are found in the sample as a whole from baseline to week 12. This will reduce the number of exploratory tests undertaken. Differences from baseline to week 12 will be investigated by paired t-tests. Primary outcomes and outcomes associated with dietary composition will also be investigated in the same manner at weeks 1, 2, 4 and 8.

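### The primary models for free-sugar intake and four key secondary outcomes adjust for Week-12 energy intake and activity, so they do not estimate the total effect of the recommendations

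*SAP*

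**What the plan says.** The SAP (Data Analysis, Analyses One) gives every primary model a core of sex, age, trial group, baseline %FS, baseline weight and the baseline value of the outcome. For five outcomes it then adds, without condition: "TEI at Week 12 and physical activity at Week 12 will also be included". The five are %FS (a primary outcome), intake of sugar-sweetened foods, intake of LCS-sweetened foods, body weight and waist circumference. Secondary models only add more terms, and for these "All variables measured will be considered as secondary variables".

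The same section lists TEI among the "key secondary outcomes - daily energy intake, sugar-sweetened food intake". It also says: "Primary outcomes and outcomes associated with dietary composition will also be investigated in the same manner at weeks 1, 2, 4 and 8".

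Protocol section 4.3 places allocation after the baseline assessments, so anything measured at Week 12 is post-randomisation. Protocol section 8 states: "Quantitative data will be analysed using SPSS, on an Intention-to-Treat basis". The SAP's multiple-imputation section says: "Main analyses were completed on an intention to treat basis".

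In protocol section 8.1 the core model is simpler: "the outcome at week 12 will be predicted by trial arm (intervention/control) and outcome variable at baseline". That section also plans further covariates where possible. Energy intake is among them, with no time point given. Physical activity is not named.

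**The concern.** Adjusting for a variable that the intervention can change alters the question. With Week-12 TEI in the model, the group coefficient compares people who ended the trial with the same energy intake. The trial asks what happens when a recommendation is handed out, including any change in energy intake that follows. Analysing everyone in the arm to which they were allocated does not cure this. The analysis set can be intention-to-treat while the coefficient is not the total effect.

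The problem is sharpest in two places. For %FS, TEI is the denominator of the outcome. For weight and waist, energy intake is a likely pathway, so the adjustment can remove the effect being sought. Neither document calls the adjusted result a direct-effect or mediation analysis, and no model without the terms is planned that would show how much they matter.

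Two related passages widen the issue. Read literally, the sentence on weeks 1, 2, 4 and 8 adjusts week-1 %FS for values recorded 12 - 1 = 11 weeks later. Protocol Table 2 schedules the activity questionnaire only at baseline and Week 12. The open candidate list for secondary models also has no limit to pre-randomisation variables.

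**Working it through.** **No plan figure to reproduce.** The documents give no expected arm effect on TEI or activity and no slopes. The only numerical anchors, in protocol section 4.2, are a 2-point target and a standardised difference of 0.8. Together they imply an SD of 2 / 0.8 = 2.5 points, derived from a saturated-fat trial.

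**Identity.** In least-squares regression on the same data, for each arm against control:

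adjusted effect = total effect - b_TEI × ΔTEI - b_PA × ΔPA

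Here b is the slope of the outcome on each Week-12 covariate in the full model. Δ is the arm difference in that covariate after adjustment for the other (baseline) terms. The shift is zero if the arms do not differ on the covariates or if the slopes are zero.

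**The sign is not fixed for %FS.** Higher TEI lowers %FS through the denominator, but TEI also contains the free sugars, so b_TEI can be negative or positive. Take an assumed total effect of -2.0 points and ΔTEI = -200 kcal:

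- slope -0.5 per 100 kcal: -2.0 - (-0.5 × -2) = -3.0
- slope +0.5 per 100 kcal: -2.0 - (0.5 × -2) = -1.0

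**Simulated %FS (TEI term only).** Assumptions: mean intake 2000 kcal with 220 kcal (11%) from free sugars; free-sugar SD 60, 80, 100 or 120 kcal; other-energy SD 200, 300 or 400 kcal; lognormal intakes; within-person correlation 0.5; entry if baseline %FS exceeds 5. Week-12 %FS was regressed on arm and baseline %FS, with and without Week-12 TEI.

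| Assumed arm effect | Total effect (points) | Adjusted for Week-12 TEI | Shift |
|---|---|---|---|
| (a) 50 kcal free sugars within a 200 kcal reduction | -1.48 to -1.54 | -2.21 to -0.55 | -0.70 to +0.97; positive in 4 of 12 SD pairs |
| (b) only the 50 kcal of free sugars falls | about -2.3 | not tabulated | -0.16 to +0.25 |
| (c) energy-neutral swap | not tabulated | equal to total | 0.0 |

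In (a), correlations of 0.3 to 0.7 and normal or lognormal intakes widen the shift to -0.95 to +1.40. Applying the reductions proportionally gives -0.68 to +1.08. The end-points therefore depend on modelling detail, but both signs recur. Replacing Week-12 TEI with baseline TEI recovers the total effect to within 0.01 in every scenario.

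**Weight.** Assume a total effect of -1.0 kg with a 200 kcal reduction. Let share s act through TEI, and let TEI be measured with reliability r. Then:

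adjusted effect = -1.0 + s × r

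- s = 1: 0.0 kg at r = 1; -0.5 kg at r = 0.5; -0.7 kg at r = 0.3
- s = 0.25: -0.75 kg at r = 1; -0.925 kg at r = 0.3

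No bias was computed for activity or for the two sweet-food outcomes.

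**The case against.** The strongest reply accepts the principle and disputes the size.

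- **The protocol already planned energy adjustment.** It did, where feasible, so fixing the time point could be called a clarification. But the protocol did not choose Week 12, and the activity term is new in the SAP. A post-randomisation value remains the wrong choice for a total effect.
- **The large shifts come from scenario (a).** The recommendations in protocol section 5 concern sugars and substitution, and none advises cutting energy. In (b) the largest shift is 0.25 / 2.3, about 11% of the effect. In (c) it is zero. This stands: the shift may turn out small.
- **The spreads are wide.** Baseline %FS SDs in the main grid run from about 2.85 to 5.3, all above the implied 2.5. With free-sugar SDs of 40 to 50 kcal, which bring the spread near 2.5, the shifts in (a) were all negative (-0.41 to -0.74). Positive shifts appeared only at SDs of about 3.6 and above. This also stands. At the protocol's implied SD the likelier distortion in (a) is an exaggerated effect, though that SD is borrowed from another nutrient.
- **The simulation is simpler than the SAP model.** It omits sex, age, baseline weight and activity. The identity does not depend on this, but the numerical ranges do.
- **The weeks 1 to 8 sentence is ambiguous.** It follows the sentence on paired t-tests and may not carry the Week-12 covariates. It needs clarifying.
- **Adherence remains.** Its model, like the one for daily energy intake, has no required Week-12 terms. That does not repair the %FS analysis.
- **Activity is the weaker case.** No arm is described as giving activity advice.

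**Conclusion.** The concern holds. As written, the primary analysis of %FS and of four key secondary outcomes estimates a difference conditional on Week-12 energy intake and activity. No unconditional model is specified for them. That does not match the intention-to-treat aim in either document.

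Confidence is high on the principle and low on the size. Whether the %FS effect would look larger or smaller cannot be told from the documents. Under the assumptions above, the shift runs from zero to about 1 point in the main grid. One point is half the 2-point difference the trial was designed to detect. For weight and waist, an effect that acts through lower energy intake would be partly or wholly adjusted away. Because this affects a primary outcome and is easily corrected, it should be fixed before the results are interpreted.

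**What to change.** In Analyses One, replace the two Week-12 terms with TEI and physical activity measured at baseline for the five outcomes, or remove them. Both baseline values exist: energy intake is in the SAP's imputation sequence and the activity questionnaire is in protocol Table 2. State that the week 1, 2, 4 and 8 models use the same baseline terms. Limit candidates for the secondary models to variables measured before randomisation. Keep any Week-12-adjusted model only as a labelled exploratory or mediation analysis.

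A minor consistency point can be settled in the same edit. The SAP treats body weight as a randomisation variable, but protocol section 4.3 stratified on BMI. Enter baseline BMI as the stratification covariate. In the weight model, say that BMI and baseline weight both stay in even if their correlation exceeds the SAP's 0.7 cut-off. This does not change the effect being estimated.

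The cost is SAP wording and a re-run with different covariate columns, with no new data. Some residual variance explained by Week-12 TEI is given up. Across versions of the simulation, the standard error of the %FS arm effect with baseline TEI ranged from 10% smaller to 15% larger than with Week-12 TEI.
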